## **12.0 SUBJECT WITHDRAWAL**

The subject is free to withdraw from this study at any time. The subject must inform the Investigator immediately if they intend to withdraw. To terminate the subject's participation in this study, they must contact the Investigator at the contact information listed on page one of the informed consent form. They will be asked to come to the study clinic or Investigators office to complete a final follow up visit and may be asked to perform end of study procedures. Their decision to participate in this study or to withdraw from this study will not influence the availability of their future medical care and will involve no penalty or loss of benefits to which they are otherwise entitled.

The Investigator in charge of the study can remove the subject from this study without their consent for any reason, including, but not limited to:

- a) His/her judgment that any condition or circumstance may jeopardize their welfare or the integrity of the study.
- b) Their failure to follow the instructions of the Investigator(s).
- c) If the study is stopped by the sponsor and/or Investigators participating in the study prior to completion.

Data collected prior to withdrawal will be used in data analysis but after withdrawal no further data will be collected.

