**2.11 Replacement of Subjects**

Replacement of subjects who have withdrawn or been withdrawn from the study will be allowed to be replaced with prior approval from the sponsor and/or IRB.

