## **2.14 Adverse Event Recording**

All data captured must be supported by the Investigator's timely assessment and documentation of the adverse event in the case report forms or source documents. All documented adverse events will be reviewed by the Sponsor or designee to determine whether the adverse event meets regulatory reporting requirements and to ensure timely adverse event reporting to meet local and global regulatory requirements. All adverse events must be followed until their resolution.

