#### 2.15.3 Patient Populations

Interim results may be collected and reported. All data will be analyzed at the end of the study. The primary analysis will be performed by the intention-to-treat approach. Everyone who begins the treatment is part of the study whether he or she completes the study or not. Additional per-protocol analysis may also be performed on subjects assigned to Group A who complete the entire clinical trial according to the protocol. The most appropriate method of handling missing values will be chosen based on the individual trial goals, endpoints and context.

The analysis of demographic, medical history, and efficacy variables will be based on all patients who are randomized and receive at least one treatment. The analysis of safety data will be based on all patients who receive at least one treatment, and have at least some safety data.

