Adverse events, whether serious or non-serious, will be followed until the condition is resolved, stabilized, otherwise explained or the subject is lost to follow-up. Adverse events will be captured throughout the study and where appropriate, medical tests and examinations will be performed to document the resolution of event(s). Outcomes may be classified as resolved, improved, unchanged, worse, fatal, unknown or lost to follow-up. Following the resolution of any study-associated adverse events there will be no further adverse event reports for that subject.

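### Section 12.0 ends data collection at withdrawal, while Sections 2.14 and 14.0 require adverse event follow-up with no exception for withdrawal, so late or lasting effects in leavers can go uncounted

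*Combined protocol and SAP*

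**What the plan says.** Section 12.0 (Subject Withdrawal) describes two routes out of the study. A subject may leave by choice, and of these subjects it says "They will be asked to come to the study clinic or Investigators office to complete a final follow up visit", adding that end-of-study procedures may be requested. The investigator may also remove a subject without consent. The listed reasons include "His/her judgment that any condition or circumstance may jeopardize their welfare or the integrity of the study", failure to follow instructions, and "If the study is stopped by the sponsor and/or Investigators participating in the study prior to completion". The section then ends: "Data collected prior to withdrawal will be used in data analysis but after withdrawal no further data will be collected".

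The adverse event sections set different limits. Section 2.14 states "All adverse events must be followed until their resolution". Section 14.0 states "Adverse events, whether serious or non-serious, will be followed until the condition is resolved, stabilized, otherwise explained or the subject is lost to follow-up", and an earlier paragraph of that section gives the same list.

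Four other places bear on the point:
- Section 1.2 makes adverse events and side effects the primary objective.
- Section 2.15.3 says "Everyone who begins the treatment is part of the study whether he or she completes the study or not". It bases the safety analysis on treated subjects who have some safety data.
- Section 11.0 asks a subject removed for pregnancy to have a final evaluation and allows the pregnancy to be tracked.
- Section 22.0 lets the sponsor or the investigator discontinue the study, the latter for safety, and gives no rule for follow-up afterwards.

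**The concern.** The closing sentence of Section 12.0 is an instruction that sites will act on, and it limits the data behind the primary outcome. Section 2.14 ends follow-up at resolution. Section 14.0 allows four end points. Neither lists withdrawal, and being lost to follow-up is a different thing from leaving by choice or being removed.

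The timing matters for this device. Section 2.14 anticipates scarring, nodules, hardness and prolonged swelling or redness. The onset or final outcome of these may come after treatment has stopped. Section 3.3 says the device is not cleared and has limited safety data. Section 2.15.1 judges success by whether the physician finds the side effect profile acceptable, and Section 2.15.6 reports numbers and percentages of subjects. A leaver counts in the denominator of those percentages but can add nothing to the numerator after the last contact. The judgement of acceptability could then rest on a profile that is incomplete for late effects, with nothing in the tables to show it.

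**Working it through.** There is no stated figure to reproduce. The target of 20 subjects in Section 2.15.2 comes with no event rate, dropout rate or precision target. The check is therefore a comparison of texts, followed by an illustration of scale.

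**Step 1: the rules applied to one open event.** Take a treated subject with an unresolved skin reaction who decides to leave.

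| Section | What it requires |
|---|---|
| 2.14 | Follow until resolution |
| 14.0 | Follow to one of four end points; withdrawal is not among them |
| 12.0, mid-section | Request a final visit |
| 12.0, last sentence | Collect nothing after withdrawal |

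The final visit can be squared with the last sentence by reading the two in sequence: exit visit first, then no more data. Sections 2.14 and 14.0 cannot be squared with it if the reaction is still open after that visit, or if the subject declines the visit. An event that first appears after the last contact falls in the same gap.

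**Step 2: who the rule covers.** The last sentence of Section 12.0 speaks only of withdrawal. Within that section, the subject withdraws and the investigator removes. Section 2.11, however, has "Replacement of subjects who have withdrawn or been withdrawn from the study", which uses the same verb for both routes. Covering removal, and through the listed reasons a stopped study, is thus a fair reading that the text does not state. Section 11.0 points the other way for one kind of removal, since it asks for an evaluation afterwards.

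**Step 3: direction.** Events recorded before leaving are kept. Events after the last contact are not observed. For late or lasting effects, the observed count is therefore at or below the true count, over an unchanged denominator.

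**Step 4: scale (illustration; the number of leavers w is assumed).** N is 20 (Section 2.15.2) or 30 (the maximum in Section 2.1). The share of subjects whose late-event status is unknown is w/N. If no late event is seen among the N − w subjects followed throughout, the one-sided 95% upper bound on the late-event rate is 1 − 0.05^(1/(N − w)). This bound assumes that leaving is unrelated to late events.

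| w | N = 20: w/N | N = 20: bound | N = 30: w/N | N = 30: bound |
|---|---|---|---|---|
| 0 | 0% | 13.9% | 0% | 9.5% |
| 2 | 10% | 15.3% | 6.7% | 10.1% |
| 4 | 20% | 17.1% | 13.3% | 10.9% |
| 6 | 30% | 19.3% | 20% | 11.7% |

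If leaving is related to harm, the bound no longer holds, and the w/N column gives the largest share of subjects whose late events could be missed.

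**Step 5: a hypothetical extreme, for late sequelae only.** Suppose 3 of 20 treated subjects leave and each later has a lasting effect that is not seen at any exit visit. The true rate is 3/20 = 15% (Clopper-Pearson 95% interval 3.2% to 37.9%). The sequela line of the table could read 0/20 = 0% (0% to 16.8%). Reactions that occurred before these subjects left would still be in the table.

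**The case against.** The best defence is that the gap is narrow. Leavers are asked for a final visit, so the ordinary reading of Section 12.0 is an exit assessment followed by closure. Earlier data are kept. Section 14.0 provides outcome categories, including unchanged, worse and unknown, so an open event can be reported with its last status. The safety analysis is descriptive, so no test or threshold depends on the missing data.

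Most of this stands, and it rules out several stronger readings:
- **That all data collection stops the moment a subject leaves.** The requested final visit and the evaluation in Section 11.0 contradict this.
- **That the rule certainly ends collection for removed subjects, or for everyone when the study is stopped.** Section 12.0 does not say so, and Section 22.0 contains no data cut-off.
- **That the subjects cut off are those most likely to have been harmed.** Removal on welfare grounds makes this plausible. The other listed reasons include not following instructions and a stopped study, and the documents give no data on why subjects leave.
- **That the intention-to-treat statement is defeated.** Section 2.15.3 defines who is included, and leavers remain included with their earlier data. Their absent later visits are a missing-data matter, which that section mentions separately.

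The defence does not remove the conflict. The final visit is a request, Section 12.0 does not extend it to removed subjects, and one visit cannot follow an event that is still open afterwards. An outcome code records the last status but does not settle whether the site may continue to follow the event.

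**Conclusion.** The point holds in a limited form. Section 12.0 conflicts with Sections 2.14 and 14.0 for adverse events that are open at, or begin after, a leaver's last contact. It is also silent on whether its rule reaches removal by the investigator or a stopped study. Because adverse events are the primary objective and leavers stay in the safety denominator, the possible error in late or lasting effects runs in one direction, toward under-counting.

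Its size cannot be established. The documents give no withdrawal rate, no reasons for leaving and no event rates. In a study of 20 to 30 subjects, each subject cut off is 5% (1/20) to 3.3% (1/30) of the safety set. The tabulated ranges rest on assumed numbers of leavers. The 0% against 15% contrast is a hypothetical extreme confined to late sequelae; a reader might take it as a claim about adverse events overall, which it is not.

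**What to change.** Replace the last sentence of Section 12.0 with a rule that separates leaving treatment from withdrawing consent to data collection:

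1. Data collection ends only when the subject withdraws consent to it.
2. For subjects who stop treatment, are removed by the investigator, or are in the study when it is stopped, safety data collection continues. The minimum is an adverse event contact at the 30 and 90 day times already in the schedule, where feasible. Open events are followed to the end point in Section 14.0.
3. For every subject who leaves, record the reason and the last known outcome of each open event, and report these with the safety summary.
4. Reconcile Sections 2.14, 11.0, 12.0, 14.0 and 22.0 into one end-of-follow-up rule that states how it applies to withdrawal, removal and study termination.

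Full 30 and 90 day visits after a study stop are not needed to resolve the conflict. The cost is protocol wording, matching consent text and a few follow-up contacts. Group A already has these visits. In Group B they are optional, so a contact there may be an addition. The protocol already provides for late return in one case: Section 2.8 (Follow Up) brings back Group A subjects affected by COVID-19 within 1 year of last treatment.

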## **13.0 PHOTOGRAPHY**

Standardized photographs will be taken of the treatment area. The subject will be asked to remove jewelry, make-up, and lotions prior to each photo session. Photographs will be taken with an appropriate high-resolution digital camera. Camera settings (lighting, distance, background, polarization, etc.) will be reproduced at each visit, so that photographs are suitable for comparison. Photographs will be taken of the treatment area for study purposes. If the subject does not wish to have their photographs taken, they cannot be in the study.

## **14.0 ADVERSE REACTIONS DEFINITIONS AND REPORTING REQUIREMENTS**

All adverse events that occur, starting from the time of the first treatment, will be recorded in the source documents and Case Report Forms (CRF).

Adverse Events (AE) occurring will be captured and followed until the condition resolves, stabilizes, is otherwise explained, or the subject is lost to follow-up. Subjects will be instructed that they may contact the Investigator at any time throughout the course of the study.

The Investigator and/or designated study staff will review each event and assess its relationship to the study device (not related, unlikely, possible, probable, and highly probable). The following definitions will be used for rating relationship to the Brera/Med 400® treatments:

- Not related – The event is clearly related to other factors such as the subject's clinical state, therapeutic interventions, or concomitant medications administered to the subject.
- Unlikely – The event was most likely produced by other factors such as the subject's clinical state, therapeutic interventions, or a concomitant medication administered to the subject; and does not follow a known response pattern to the investigational product.
- Possible – The event follows a reasonable temporal sequence from the time of investigational product administration; **and/or** follows a known response pattern to the study sampling sessions; **but** could have been produced by other factors such as the subject's clinical state, therapeutic interventions, or concomitant medications administered to the subject.
- Probable – The event follows a reasonable temporal sequence from the time of investigational product administration; **and** follows a known response pattern to the investigational product; **and** cannot be reasonably explained by other factors such as the subject's clinical state, therapeutic interventions, or concomitant medications administered to the subject.

- Highly Probable – The event follows a reasonable temporal sequence from the time of investigational product administration; **and** follows a known response pattern to the investigational product; **and** cannot be reasonably explained by other factors such as the subject's clinical state, therapeutic interventions, or concomitant medications administered to the subject; **and** either occurs immediately following investigational product administration, **or** improves on stopping the investigational product, **or** reappears on repeat exposure, **or** there is a positive reaction at the application site.

Each adverse event reported will be graded on a 3-point severity. Using the following definitions for rating severity will be used:

- Mild – easily tolerated, causing minimal discomfort, and not interfering with normal everyday activities.
- Moderate – sufficiently discomforting and may interfere with normal everyday activities.
- Severe – incapacitating and/or preventing normal everyday activities.

**A Serious Adverse Event (SAE)** is any adverse device experience that results in any of the following outcomes: death, a life-threatening adverse device experience, in-patient hospitalization or prolongation of hospitalization, a persistent or significant disability/incapacity, or a congenital anomaly/birth defect. Important medical events that may or may not result in death, be life-threatening, or require hospitalization may be considered a serious adverse device experience when, based upon appropriate medical judgment, they may jeopardize the subject or subject may require medical or surgical intervention to prevent one of the outcomes listed in this definition

If any of the above adverse events are serious as defined by the FDA Code of Federal Regulations (CFR), Title 21, special procedures will be followed. All serious adverse events will be reported within 24 hours of acknowledgment to the Sponsor whether or not the serious events are deemed sampling session-related. All serious event reporting will adhere to 21 CFR part 812 and the IRB will be notified accordingly.

The SAE information will be entered into the database and a desk copy of the complete SAE report will be submitted to the study file.

Adverse events, whether serious or non-serious, will be followed until the condition is resolved, stabilized, otherwise explained or the subject is lost to follow-up. Adverse events will be captured throughout the study and where appropriate, medical tests and examinations will be performed to document the resolution of event(s). Outcomes may be classified as resolved, improved, unchanged, worse, fatal, unknown or lost to follow-up. Following the resolution of any study-associated adverse events there will be no further adverse event reports for that subject.

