#### **Reporting Adverse Events:**

Report	Submit To	Description/Constraints
--------	-----------	-------------------------

Adverse Events, Unanticipated Adverse Device Effect	IRB and Sponsor	If an unforeseen complication is determined to be an unanticipated adverse device effect, the investigator's report must be submitted within 10 working days after the investigator first learns of the effect.
Serious Adverse Events	IRB and Sponsor	The sponsor must be notified within 24 hours of serious adverse events. The IRB must be notified within 1 working day of serious adverse events as defined by FDA guidelines.

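### Section 14.0 ends adverse event reports per subject rather than per event, contradicting the capture and serious-event rules around it

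*Combined protocol and SAP*

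**What the plan says.** Section 14.0 (Adverse Reactions Definitions and Reporting Requirements) ends its paragraph on follow-up and outcome of events with: "Following the resolution of any study-associated adverse events there will be no further adverse event reports for that subject". No other text limits this sentence to the event that resolved, or to the time after the last visit.

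Other statements point the opposite way:

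- Two sentences earlier in the same paragraph: "Adverse events will be captured throughout the study".
- At the start of Section 14.0: "All adverse events that occur, starting from the time of the first treatment, will be recorded". No end point per subject is given.
- On serious events, Section 14.0 says: "All serious adverse events will be reported within 24 hours of acknowledgment to the Sponsor", whatever their relationship to treatment.
- The Reporting Adverse Events table repeats this ("The sponsor must be notified within 24 hours of serious adverse events") and gives the IRB limit as 1 working day. It allows 10 working days for the investigator's report "If an unforeseen complication is determined to be an unanticipated adverse device effect".
- Section 2.12 has an adverse event row for both groups, marked at screening, treatment visits, the optional call and both follow-up visits (optional visits in Group B).
- Section 1.2 names adverse events and side effects over the whole study as the only primary objective. Section 2.15.6 bases the safety summaries on events collected over the same period.

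**The concern.** A site reading Section 14.0 finds two instructions that cannot both be followed once a subject has had an event and recovered from it. One says to keep capturing and reporting. The other says reports for that subject are finished.

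This situation could arise early. Section 2.14 lists mild swelling, soreness, cramping and redness as possible effects and describes treatment discomfort as usually temporary. Group A subjects may have up to 8 treatments, so a mild effect that clears after the first could be followed by many more exposures. Section 21.0 allows no departure from the protocol without sponsor approval except in a medical emergency, so the site should not be left to choose which rule to ignore.

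The data affected are those for the primary objective. Section 2.15.1 ties study success to whether the physician finds the side effect profile acceptable, and Section 3.3 says the device has limited safety data.

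**Working it through.** The plan states no figure on this point, so the check is a comparison of texts followed by a count from the visit schedule.

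**1. Unit of each rule.** Recording, causality review, severity grading and follow-up in Section 14.0 all work per event. Events are "captured and followed until the condition resolves, stabilizes, is otherwise explained", which closes the condition and not the subject. Only the disputed sentence closes the subject.

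**2. Direct conflicts.** Take a subject whose redness after treatment 1 has resolved and who has a skin burn after treatment 6.
- Opening of Section 14.0: the burn is recorded. Disputed sentence: no report.
- Section 2.12: adverse events are assessed at that visit and later ones. Disputed sentence: nothing further to report.
- If the burn were serious or an unanticipated device effect, the reporting table would require notice to the sponsor and IRB. Disputed sentence: no report.

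**3. Implied conflict.** One of the four alternative criteria that can complete a Highly Probable rating is that the event "reappears on repeat exposure". That criterion can be used only if an event may be reported after it has first gone away. The protocol has no separate rule on reporting recurrences, so this is supporting evidence only.

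**4. Does a milder reading remove the conflict?**
- *Reports means submissions to sponsor or IRB only.* Recording then continues and the analysis data stay complete. The conflict with the reporting table remains, because that table requires exactly such submissions without this exception.
- *The plural means once all events so far have resolved.* The stop comes later, but it can still fall before further treatments.
- *Only the resolved event is closed.* This removes the conflict, but it is not what the sentence says.

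**5. Size under the literal reading.** Inputs: Group A, all 8 treatments taken (Section 2.1), follow-up at 30 and 90 days after the last treatment (Section 2.12). If an event following treatment k resolves before treatment k + 1, the treatments left without reports number 8 − k.
- k = 1: 8 − 1 = 7 treatments and both follow-up visits.
- k = 4: 8 − 4 = 4 treatments and both follow-up visits.
- k = 8, resolved before the 30-day visit: 8 − 8 = 0 treatments, but both follow-up visits.

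The first case is the maximum. It is not assured: treatments are 7 ± 4 days apart, so 3 to 11 days, and Section 2.14 also lists twitching that may last days and prolonged swelling and redness.

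**6. Effect on the planned summaries.** Section 2.15.6 reports the number and percentage of patients for each outcome. A subject's first event is recorded under every reading, so the percentage with any event does not change. A different event arising after the stop would be missing, so the percentage with that outcome, and the total count of events, could be too low.

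**The case against.** The strongest reply is that nobody would apply the sentence literally. It closes a paragraph about following events to their outcome, continued capture is stated two sentences before it, and every scheduled visit has an adverse event row. There is a single centre, with sponsor training and case report form review (Section 5.0). The intent was very likely to end follow-up of a resolved event. This stands as an argument about likelihood: the practical loss may well be nil. It does not make the text consistent.

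A second reply separates recording from reporting: if reports are submissions, the data for the primary objective are intact. That also has force, and it would remove the effect on the analysis. It is not certain, because Section 14.0 also uses the word for ordinary events when it introduces the severity grading. Even if accepted, it leaves the clash with the reporting table.

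A third reply is that the protocol does name a governing standard for the gravest category: Section 14.0 places serious-event reporting under 21 CFR part 812, and Section 17.0 requires conduct under FDA regulations. This is correct, so it would be wrong to say that the rules are left wholly unranked. It does not settle the matter for non-serious events, which are most of the effects Section 2.14 anticipates.

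**Conclusion.** The inconsistency is real and should be corrected. As worded, a rule bearing on the sole primary objective contradicts the capture, visit and safety-reporting rules around it, and no milder reading that keeps to the sentence's words removes every conflict.

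The size is limited to this. If the sentence is applied literally, all 8 treatments are given and an event resolves between treatments 1 and 2, then up to 7 of 8 Group A treatments and both follow-up visits could go without reports. Event counts and the percentage of subjects with a specific later event could be understated; the percentage with any event could not. At a site that records everything from first treatment, the loss is zero.

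A reader might infer that most of the safety data would be lost, for example from calendar time. The nominal span from treatment 1 to the 90-day visit is 7 × 7 + 90 = 139 days, of which 6 × 7 + 90 = 132 follow treatment 2. The documents do not support that inference. The day count depends on when the event resolves (one day after treatment 1 would leave 138 of 139), so it is not a bound, and days are not events. Nor can a share of events lost be given, because the documents state no event rates and any such percentage would simply reflect an assumed rate.

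**What to change.** Replace the sentence with per-event wording, for example: *Once follow-up of an adverse event has ended, no further reports are needed for that event; new or recurrent events, including serious ones, continue to be recorded and reported for every subject through the last study visit.*

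Separately, Section 2.14 requires every event to be followed to resolution, while Section 14.0 also lets follow-up end when the condition stabilizes or is otherwise explained, or when the subject is lost. These statements differ on when follow-up ends and should be reconciled, since the replacement sentence depends on that definition.

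The cost is one replaced sentence and one aligned definition in a protocol amendment, with the IRB approval that Section 21.0 requires. No visit, contact, test or analysis is added.
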